Appendix A: Cardiac CT Imaging Protocol Guidelines[†]

Cardiac CT Imaging: Diagnostic Intervention to Be Tested

Equipment

Cardiac CT imaging will be performed using at least 64-slice CT scanner technology according to the vendor specific protocol for the evaluation of the coronary arteries and LV function (Table 2).

Table 2. Overview of vender-specific protocols as used in the proposed trial

CT Scanner	Spatial Resolution/ Slice Collimation	Gantry Rotation Time/ Temporal Resolution	Tube Voltage, Tube Current	Estimated Radiation Exposure (mSv)*
Siemens Definition Dual Source 64-row MDCT	2 x 64 x 0.6 mm	330 ms/83 ms	100-120 Kvp, 850 effective mAs	7-15 mSv
Toshiba Acquillion 64-row MDCT	64 x 0.45 mm	400 ms/200 ms	100-120 Kvp, 700 mAs	10-14 mSv
Siemens Somatom 64-row MDCT	64 x 0.6 mm	330 ms/165 ms	100-120 Kvp, 850 mAs	7-14 mSv
GE Lightspeed VCT 64-row MDCT	64 x 0.6 mm	350 ms/175 ms	100-120 Kvp, 750 mAs	11-17 mSv
Philips Brilliance iCT 256-row MDCT	64 x 0.624mm	270 ms/135 ms	100-120 kVp, 850 mAs	7-13 mSv

* includes radiation exposure from CAC imaging, assumes the use of tube modulation. Actual radiation doses will depend on the subjects' body habitus, as well as the rate and regularity of the heart during acquisition.

Image Acquisition

Based on preliminary data from the clinical sites, the image acquisition takes approximately 20 minutes. The participant will be transported to the CT suite and returned by qualified study personnel. Continuous heart rate and rhythm will be monitored during the study exam with 4-lead ECG electrodes. Blood pressure and heart rate will be measured before and after the study exam.

General recommendations include:

- Minimal flow rate: 5ml/sec
- Retrospective ECG triggering with use of tube modulation techniques to permit assessment of LV function

[†] This appendix is intended as example of a cardiac CT imaging protocol. Please refer to the current version of the Massachusetts General Hospital Cardiovascular Imaging Core Laboratory (CVIC) Study Imaging Procedure for ROMICAT II study imaging procedures.

- Prospective triggering in subjects with appropriate conditions, to further minimize radiation exposure.
- 100 kVp if BMI <30 kg/m²
- 120 kVp if BMI > 30 kg/m²

In general the image acquisition protocol consists of the following 3 steps:

Step 1—Participant Preparation: Participants will be instructed and trained in breath holding. ECG electrodes will be mounted on the chest to enable co-registration of image acquisition and ECG signal. At sites WITHOUT a dual source computed tomography (DSCT) scanner, all participants with a heart rate >65 beats per minute will receive beta blocker (5 to 20 mg Metoprolol, I.V.) to optimize image quality and 600 mcg sublingual nitroglycerin to maximally dilate the coronary arteries unless their systolic blood pressure is <100 mm Hg or other contraindications are present.⁴³ At sites with a DSCT scanner, due to the improved temporal resolution, beta blockers are not required though may be given and participants will receive sublingual nitroglycerin if there are no contraindications.

Step 2—Image Acquisition: All image acquisitions will be performed during a breath hold on inspiration with the following acquisitions:

- a. Topogram**—The cardiac CT imaging protocol will start with a topogram of the chest permitting the localization of the position of the heart.
- b. Noncontrast calcium score scan**—A prospective gated low dose non-contrast CT scan (100 kVp for BMI<30, or 120 kVp for BMI >30, 320 mA), with scan initiation at 70% (Siemens scanners) or 75% (all other manufacturers) of the RR-interval, will be performed.⁴⁴ Contiguous 2.5 to 3 mm images will be acquired to quantify the presence and amount of coronary artery calcification.
- c. Contrast-enhanced CT angiography**—Image acquisition will conclude with a contrast-enhanced CT scan to evaluate the presence of coronary atherosclerotic plaque, significant coronary artery stenosis, and global and regional LV dysfunction. For this scan, on average 90 mL of contrast will be injected as a bolus at a rate of 5-6 mL/s to opacify the lumen of the coronary arteries, the aorta and the left ventricle. Appropriate timing of the contrast bolus will be ensured by either the determination of the transit time or the bolus trigger technique. Scanning will be performed continuously throughout the cardiac cycle. Using ECG gating, the tube current will be reduced during systole according to each manufacturer's specific protocol to minimize radiation exposure. Alternatively, in subjects where prospective triggering is appropriate, it may be performed, per the manufacturer's specific protocol to further reduce radiation exposure.

Step 3—Image Reconstruction: The following data sets will be reconstructed immediately after the scanning on a dedicated offline work station: 1) axial images from the non-contrast-enhanced scan for the quantification of CAC (pixel matrix: 512 x 512, field of view [FOV]: 25 cm); 2) two end-diastolic and one end-systolic data set (0.5-0.75 mm thick axial images, 50% overlap) from the contrast-enhanced CT scan for the

detection of coronary plaque and stenosis (pixel matrix: 512 x 512, FOV: 25 cm); 3) one multiphase reformatted dataset of 1.5 mm thick axial images at 10% increments (10 phases) for single source CT scanners or 5% increments (20 phases) for dual-source CT scanners throughout the cardiac cycle from the onset of the R-wave for the assessment of global and regional LV function in a cine mode and 4) a full field of view with 3 mm thick axial images, covering the portions of the thorax acquired during the cardiac CT scan, for the assessment of major incidental findings. All CT data sets will be transmitted to the CVIC Lab's picture archiving and communication system (PACS) via internet using a dedicated routing system (Code of Federal Regulatory compliant) and stored.

Image Evaluation

Reconstructed data sets will be evaluated for the presence of CAC, coronary atherosclerotic plaque and stenosis; and global and regional LV function by dedicated highly trained cardiac CT imagers using established criteria²².

Step 1—Coronary Artery Calcification: All non-contrast enhanced CT scans will be assessed for the presence of CAC. If present, the amount of CAC will be *quantified* using a dedicated semiautomatic software and expressed as an Agatston Score (AS) as described elsewhere.⁴⁵

Step 2—Assessment for Stenosis: Contrast-enhanced CT images will be *qualitatively* evaluated for the presence of coronary atherosclerotic plaque and significant coronary artery stenosis using axial data sets; thin slice (5 mm) reconstructions orthogonal and perpendicular to the vessel centerline, and short axis cross-sectional reconstructions. Assessment will include each of the major epicardial vessels (left main, left anterior descending, left circumflex, and right coronary artery) and their side branches.⁴⁶⁻⁴⁸

Step 3—Global and Regional LV Function: Global and regional LV function will be assessed visually with the multiphase reformatted dataset in cine mode to correspond to those typically used in echocardiography, including LV horizontal long-axis (4-chamber view), vertical long-axis (2-chamber view), LV outflow tract long-axis (parasternal long axis), and short-axis view. Global LV function will be reported as normal or impaired (mild, moderate, or severe). Regional wall motion (RWM) of the myocardium will be assessed to be normal or abnormal (hypokinesia, akinesia, dyskinesia, aneurysm) in short-axis segments of the LV corresponding to the AHA/ACC/ASE 17-segment model. Hypokinesia will be defined as a segment with impaired thickening and motion, akinesia by absent thickening and motion, dyskinesia as a paradoxical outward motion of the segment during systole, and an aneurysm as a segment with wall thinning and diastolic deformation. The abnormality has to be present in at least two contiguous myocardial segments or in one segment visualized in two different views.

Step 4—Major Incidental Findings: The full field of view will be assessed by a CT reader for the presence of major cardiac and non-cardiac incidental findings such as aortic dissection, pericardial effusion, pulmonary embolism, pneumothorax, or mediastinal masses.

CT Reporting

Cardiac CT Findings

The Cardiac CT Report will be reported and included in the hospital's electronic medical record, which is accessible to all treating physicians and will be the basis for in-hospital patient management. The triage and management of the patient will be at the discretion of the ED physician.

Image Submissions

The protocol-required images must be in DICOM format and submitted to the Cardiovascular Imaging Core Laboratory (CVIC) via the internet using secure File Transfer Protocol (FTP), along with an Imaging Transmittal Worksheet. The submission procedure will be detailed in the CVIC site operations manual.

Appendix B: Adjudication of Events by Clinical Events Committee

Introduction

Because patient safety is one of the concerns in a trial assessing new technology, clinical events and serious adverse events will be independently adjudicated by the Clinical Events Committee, under the direction of [name]. This committee will adjudicate events in all subjects who potentially could have a major adverse cardiovascular event (MACE), such as, death, unstable angina pectoris (UA), myocardial infarction (MI), or coronary revascularization that occur after symptom assessment at patient's initial emergency department (ED) presentation. There is a possibility that MACE will occur during index hospitalization. For example, a second episode of chest pain diagnosed as acute coronary syndrome (ACS) occurring after the chest pain the patient presented with has resolved and all diagnostic tests were negative or recurrence of symptoms with or without hospitalization and re-hospitalization with or without testing.

Definitions of Adverse Cardiovascular Events

Adverse cardiovascular events comprise cardiovascular death, MI, unstable angina pectoris (UAP), coronary revascularization and/or re-hospitalization that are distinct from the qualifying event (after patient's initial ED presentation).

Definitions of events are listed below:

Cardiovascular Death: Any sudden cardiac death, death due to acute myocardial infarction, death due to heart failure, death due to stroke, and death due to other cardiovascular causes. In addition, any death without a clear non-cardiovascular cause, or a death without known cause will be considered cardiovascular death.

MI: In Subjects with no recent revascularization in whom normal biomarkers were never elevated or have been documented to return to normal after a qualifying (or recent) MI who meet the following criteria:

- 1.) Typical cardiac biomarker rise and/or fall AND at least one of the following:
 - a) Ischemic discomfort at rest lasting ≥ 10 minutes
 - b) ECG changes indicative of ischemia (ST elevation ≥ 0.1 mV or ST depression ≥ 0.05 mV, or new T-wave inversions).

OR;

- 2.) Development of new, abnormal Q waves (≥ 30 msec in duration and ≥ 1 mm in depth) in >2 contiguous precordial leads or ≥ 2 adjacent limb leads; or increase R amplitude in V1-V3 consistent with posterior infarction.

OR;

- 3.) Pathologic findings of an acute MI

- 4) Sudden unexpected cardiac death, including cardiac arrest, often with symptoms suggestive of myocardial ischemia, accompanied by presumably new ST elevation, or new LBBB, or evidence of fresh thrombus in a coronary artery by angiography and/or at autopsy, but death occurring before blood samples could be obtained, or at a time before the appearance of cardiac biomarkers in the blood

In subjects with percutaneous coronary intervention within 48 hours, an elevation of CK-MB >3x ULN distinct from a prior event will be considered to be a procedural MI.

In subjects with CABG within 48 hours, an elevation of CK-MB > 10x ULN distinct from a prior event will be considered to be a procedural MI.

UA: An event not meeting the definition of myocardial infarction and with the following characteristics. Chest pain or anginal equivalent at rest or in accelerating pattern AND at least one of the following objective signs:

- a) New ST-segment changes
- b) New TWI
- c) Positive stress test with imaging showing ischemia
- d) Positive stress test without imaging resulting in increased anginal medication
- e) Cath \geq 70% stenosis or thrombus

Urgent Coronary Revascularization: Ischemic discomfort or equivalent meeting the following criteria:

- a) Lasting \geq 10 minutes at rest, or repeated episodes at rest lasting \geq 5 minutes, considered to be myocardial ischemia upon final diagnosis

AND;

- b) Prompting coronary revascularization during an unscheduled visit to healthcare facility or during an unplanned (or prolonged) hospitalization for these symptoms.

Note: Attempted revascularization procedures, even if not successful will be counted. Potential ischemic events meeting the criteria for myocardial infarction will not be adjudicated as urgent coronary revascularization.

Re-hospitalization: Coronary ischemia requiring re-hospitalization is defined as an event not meeting the definitions of myocardial infarction or urgent coronary revascularization: ischemic discomfort or equivalent meeting the following criteria:

- a) Lasting \geq 10 minutes at rest, or repeated episodes at rest lasting \geq 5 minutes, or an accelerating pattern of ischemic discomfort (episodes that

are more frequent, severe, longer in duration and precipitated by minimal exertion), considered to be myocardial ischemia upon final diagnosis

AND;

- b) Prompting hospitalization (including overnight stay on an inpatient unit) within 48 hours of the most recent symptoms or prolonging hospitalization if occurring during existing hospitalization.

AND;

- c) At least one of the following additional criteria for coronary artery disease and/or ischemia:
- New and/or dynamic ST-depression ≥ 0.05 mV, ST-elevation ≥ 0.1 mV, or symmetric T wave inversion ≥ 0.2 mV on a resting ECG.
 - Definite evidence of ischemia on stress sechocardiography, myocardial scintigraphy (e.g., an area of clear reversible ischemia), or ECG-only stress test (e.g., significant dynamic ST shift, horizontal or downsloping).
 - Angiographic evidence of epicardial coronary stenosis of $\geq 70\%$ diameter reduction and/or evidence for intraluminal arterial thrombus.

Note: If subjects are admitted with suspected myocardial ischemia, and subsequent testing reveals non-cardiac or non-ischemic etiology, this will not be adjudicated as meeting this definition. Potential ischemic events meeting the criteria for myocardial infarction will not be adjudicated as ischemia requiring hospitalization.

Adjudication Process

Adverse cardiovascular events (both during index hospitalization and within 28 days) will be independently adjudicated by the Clinical Events Committee (CEC). Potential events will be identified by the sites during a follow-up phone interview at 48-72 hours and 28 days. The information collected during the call will be recorded on an "Assessment of MACE" Case Report Form, which will be submitted to the Data Coordinating Center (DCC). The DCC will request de-identified medical records and source documents, supporting the adjudication of the events., including but not limited to as discharge summary, cardiac consultation notes, ECG reports, cardiac catheterization reports, biomarker laboratory values, death certificates, autopsy reports etc. The DCC will provide copies of the medical record pertaining to the index hospitalization and the potential adverse event for adjudication to the CEC. Based on the medical record review and site reported information, the adjudicator will complete an "Assessment of MACE" Case Report Form, which in turn will be submitted to the DCC.

Adjudicators are independent board certified or board eligible cardiologists, who have received formal documented training based on a CEC Charter, and will perform a composite review of the medical records to ascertain the presence or absence of MACE as defined in the CEC charter. The adjudication is performed by the TIMI (Thrombolysis In Myocardial Infarction) Study

Group CEC, which provides adjudication services for cardiovascular trials performed worldwide. Cases will be adjudicated by two independent cardiologists with an experience in cardiovascular event adjudication. In case of disagreement the adjudicators will meet, discuss the case and attempt to come to consensus. If consensus cannot be reached, a third adjudicator will cast a tie breaking vote. This is a standard, accepted technique to assess the presence of clinical events in cardiovascular trials.^{18, 55-58}

Discharge Diagnosis from Index Hospitalization

The CEC will adjudicate the accuracy of the discharge diagnosis during index hospitalization for the first eight patients for each site, followed by a random selection of 10% of the participants. Discharge diagnoses are: ACS as defined above and consistent with the ACC/AHA Guidelines⁵⁹⁻⁶¹, including MI and UA, chest pain of cardiac origin, and chest pain of non-cardiac origin with or without a clear differential diagnosis.

Clinical sites use different cut-off values and tests to determine MI diagnosis. The DCC will provide each site's biomarker cutoffs for each individual case. The CEC therefore will adjudicate events in a manner consistent application of site-specific criteria.

For each MI identified by the CEC, a Type of MI will be assigned using the following guidelines:

Type 1: Spontaneous myocardial infarction related to ischemia due to a primary coronary event such as plaque erosion and/or rupture, fissuring, or dissection

Type 2: Myocardial infarction secondary to ischemia due to either increased oxygen demand or decreased supply, e.g. coronary artery spasm, coronary embolism, anemia, arrhythmias, hypertension, or hypotension

Type 3: Sudden unexpected cardiac death, including cardiac arrest, often with symptoms suggestive of myocardial ischemia, accompanied by presumably new ST elevation, or new LBBB, or evidence of fresh thrombus in a coronary artery by angiography and/or at autopsy, but death occurring before blood samples could be obtained, or at a time before the appearance of cardiac biomarkers in the blood

Type 4a: Myocardial infarction associated with PCI

Type 4b: Myocardial infarction associated with stent thrombosis as documented by angiography or at autopsy

Type 5: Myocardial infarction associated with CABG

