5.1 Index Hospitalization

Standard of Care Arm: Subjects will be evaluated according to each hospital's specific protocol to evaluate and manage patients with acute chest pain. Typically, the standard evaluation in the ED will include the past and current medical history, a physical examination, an ECG and a cardiac biomarker (Troponin and CK-MB) as well as other routinely obtained blood testing. Patients may undergo cardiac CT as part of SOC but only as a secondary diagnostic test. Patients in the CT arm may undergo further diagnostic testing as well.

All admitted subjects will undergo each hospital's standard rule out myocardial ischemia protocol. This protocol typically consists of observation and monitoring including serial ECGs and repeated cardiac biomarker measurements as well as a noninvasive stress test (often imaging based) to evaluate for myocardial ischemia. The participating clinical sites perform routinely either nuclear perfusion imaging [SPECT] at rest and stress, and/or stress echocardiography, and/or exercise treadmill test [ETT]. Depending on the results, subjects may undergo additional noninvasive or invasive testing (coronary angiography), and/or coronary revascularization during their hospital stay.

Interventional Arm: In subjects randomized to the intervention arm, a contrast enhanced cardiac CT will be performed (after initial troponin level is available) in addition to the initial ED evaluation.

The ED physicians will resume care of the patient and make all clinical decisions for further care of the patient (e.g., need for further evaluation or admission) based upon their cumulative clinical assessment of the patient, including findings revealed on the CT scan.

In addition, in patients from both study arms who consented to a blood draw, we will obtain three fifteen (15) mL venous blood samples over a six-hour period, less than forty-five (45) mL in total. Blood samples will be centrifuged and frozen for future analysis for cardiac-related markers.

All diagnostic tests will be performed per Society Guidelines. Cardiac Computed Tomography is performed in accordance with best practice standards as delineated in the imaging guidelines of the Society of Cardiovascular Computed Tomography by competent⁶³ and appropriately credentialed physicians. This includes the optimization of the scan protocol to limit radiation exposure.

5.2 48-72 Hour Follow up after ED discharge

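### MACE adjudicators receive the index-stay record, which in the CT arm would hold or refer to the CT report, and the protocol states no masking of arm or CT result

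*Protocol*

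**What the plan says.** Protocol Appendix B, Adjudication Process, sets out what the Clinical Events Committee (CEC) sees. The coordinating center obtains the material: "The DCC will request de-identified medical records and source documents, supporting the adjudication of the events". It then passes it on: "The DCC will provide copies of the medical record pertaining to the index hospitalization and the potential adverse event for adjudication to the CEC". The adjudicator completes the MACE form from that record and from information reported by the site. On the readers themselves: "Cases will be adjudicated by two independent cardiologists with an experience in cardiovascular event adjudication". They are trained on a CEC charter, which is not part of the document, and a third reader breaks ties.

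Appendix A, CT Reporting, says where the CT result goes: "The Cardiac CT Report will be reported and included in the hospital's electronic medical record". There it is "accessible to all treating physicians and will be the basis for in-hospital patient management".

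Section 5.1 separates the arms by this test. In the interventional arm "a contrast enhanced cardiac CT will be performed (after initial troponin level is available) in addition to the initial ED evaluation". In the standard-of-care (SOC) arm: "Patients may undergo cardiac CT as part of SOC but only as a secondary diagnostic test".

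The Study Overview and sections 3.2 and 7.2 compare 28-day MACE between arms, with similar rates as the hypothesis. Sections 7.2 and 11 name mistaken discharges as the primary safety issue.

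**The concern.** Removing patient identifiers does not remove the arm, and being independent of the sites does not make a reader blind. Followed as written, the process hands the adjudicator a record that shows whether the patient had the randomized test and what it found. No section of the protocol removes either fact.

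The trial is open to treating staff, so masked adjudication is the main available protection for the MACE comparison. A reader who has seen a normal CT may lean towards a non-ischemic cause for later chest pain, and one who has seen plaque or stenosis may lean the other way. Most SOC records would carry no such cue. The comparisons at stake are 28-day MACE between arms and missed ACS among patients sent home from the CT arm.

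**Working it through.** **1. Is masking stated anywhere?** In the protocol, blinding is mentioned only for the preceding observational study (section 2). Appendix B offers de-identification, independence, two readers and a tie-breaker. None of these conceals arm or CT. The examples of source documents in Appendix B do not name the CT report, but the list is open-ended and includes the discharge summary, which would be expected to mention a test that guided management.

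**2. How well would a CT in the record identify the arm?** Let s be the share of the CT arm scanned and c the share of the SOC arm with a CT. The protocol gives neither, so both are assumptions. With equal numbers of cases from each arm:

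- P(CT arm | CT in record) = s / (s + c)
- P(SOC | no CT in record) = (1 − c) / [(1 − c) + (1 − s)]

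| c | P(CT arm given CT), s = 100% | same, s = 95% | P(SOC given no CT), s = 100% | same, s = 95% |
|---|---|---|---|---|
| 0% | 100% | 100% | 100% | 95.2% |
| 5% | 95.2% | 95.0% | 100% | 95.0% |
| 10% | 90.9% | 90.5% | 100% | 94.7% |
| 20% | 83.3% | 82.6% | 100% | 94.1% |
| 30% | 76.9% | 76.0% | 100% | 93.3% |

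For example, 0.95 / (0.95 + 0.30) = 76.0%. The arm can usually be inferred, though not with certainty.

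**3. Where do the definitions leave room for judgement?**

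- Urgent revascularization and re-hospitalization both turn on whether the discomfort was finally judged ischemic. The re-hospitalization wording, for an accelerating pattern, covers episodes that "are more frequent, severe, longer in duration and precipitated by minimal exertion), considered to be myocardial ischemia upon final diagnosis".
- Every event must be separate from the one that brought the patient in.
- A death counts as cardiovascular unless a non-cardiovascular cause is clear.

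Against this, unstable angina also needs at least one of an ECG change, a positive stress test or a catheterization finding. Re-hospitalization needs ECG, stress or angiographic evidence, and urgent revascularization needs an attempted procedure. Biomarker-defined MI is less exposed.

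**4. How much could one reclassified event matter?** The protocol states no 28-day MACE rate. Assuming 1% to 2%, an arm of 500 has 5 to 10 events. One reclassified event is then 1/10 to 1/5, or 10% to 20%, of that arm's events, and 1/500 = 0.2 percentage points of its rate.

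For missed ACS, section 7.2 assumes 32% direct discharge in the CT arm: 0.32 × 500 = 160. This denominator reproduces the protocol's 80% chance of seeing at least one event at a true rate of 1%: 1 − 0.99^160 = 80.0%. With 0 events in 160, the one-sided 95% upper bound is 1 − 0.05^(1/160) = 1.9%. With 1 event, the exact bound solves (1 − p)^160 + 160p(1 − p)^159 = 0.05, giving 2.9%.

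**The case against.** The strongest reply is that unblinded adjudication is inferred from silence. The CEC charter governs training and definitions and may fix packet contents and redaction. This stands as a limit: a reader might infer that adjudication is in fact unblinded, but the document shows only that no masking is stated. It does not remove the point, because the protocol itself prescribes what adjudicators receive.

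A reader might also infer that adjudicators never need the CT. The text does not support that. Appendix B includes index-stay events, and its example turns on all diagnostic tests having been negative, which in the CT arm includes the CT. Its re-hospitalization note excludes cases where testing shows a non-ischemic cause, and CT could supply one, such as pulmonary embolism. Blanket redaction could therefore remove evidence that the definitions call for. This stands and shapes the remedy.

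The objective signs, the two readers and the tie-breaker narrow the scope for bias. That stands too, although two readers who have seen the same CT share the same cue.

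Finally, masking adjudicators would not reach the sites, which know the arm and identify potential events, or the CT-informed decisions that generate further tests. That is correct, and it limits what the change can achieve.

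**Conclusion.** The point holds in a limited form. As written, the protocol gives adjudicators a record that would usually reveal the arm and, where a CT was done, its result. It states no masking. The conclusion is conditional on the charter not adding it.

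Exposure is confined to the judgement elements of MACE in the 28-day between-arm comparison and to missed ACS after CT-arm discharge. The primary endpoint, length of stay, does not pass through adjudication and is unaffected.

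The size of any bias cannot be computed from the protocol. The figures show only sensitivity to a single event: 10% to 20% of an arm's events if the 28-day rate is 1% to 2%, and an upper bound of 2.9% rather than 1.9% for missed ACS with 160 discharges. A reader might infer that one reclassified event would decide the safety conclusion, but the protocol sets no decision rule that would make it so. Nor is the net direction known for MACE overall. Only after a normal CT is the pull plainly towards no event. The protocol should be amended, with moderate priority.

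**What to change.** In Appendix B, Adjudication Process:

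- State that CEC adjudicators are masked to treatment assignment. If the charter already provides this, one sentence citing it settles that part.
- For post-discharge events (those found at the 48-72 hour and 28-day contacts), redact the assignment, the index CT report and references to it from the packet, including the site-reported information, before the MACE form is completed. Do this in both arms, since SOC patients may also have a CT. Keep the rest of the index record, which is needed to judge whether the event is a new one.
- For index-stay events, MI typing and the discharge-diagnosis review, allow CT to be released where the definitions need it, after a first masked read where feasible.
- Record any case in which an adjudicator became aware of the arm.

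The cost is a new redaction step. The coordinating center asks for records already de-identified, so searching notes for mentions of CT would be extra work, on what should be a small number of cases. Masking will be imperfect where notes discuss the CT throughout, and it leaves site-level event identification and CT-driven testing untouched.
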